#### **Analysis of Secondary Objectives**

As support for the primary objective, overall DFS and 2-year DFS will be compared using the same techniques above using only the subjects in the randomized part of the study. One-year DFS will be tested using the test described above for 2-year DFS. Safety and tolerability variables will be tabulated separately for the two groups. Incidences of selected adverse events from the two treatment arms may be compared using Fisher's Exact tests on an exploratory basis. OS will be compared between treatment groups using the same methodology as DFS. PK levels will be described using summary statistics. In addition characteristics of tumor specimens and genomic DNA will be correlated with PARP inhibition, recurrence and toxicity. Continuous measures will be correlated with binary variables (e.g. recurrence and toxicity) using maximal chi-square tests and continuous variables (e.g. PARP inhibition) using Pearson or Spearman correlations. Binary variables such as tumor and genomic characteristics will be correlated recurrence and toxicity using chi-square or Fisher's Exact test. All of the analyses with the PK and correlative data are exploratory and are designed to complement efforts in other trials with this agent.

[figure not shown]
**PARP Inhibition after Preoperative Chemotherapy in Patients with Triple Negative Breast  
Cancer (TNBC) or ER/PR + and HER2 negative with known BRCA1/2 Mutations:  
Hoosier Oncology Group BRE09-146**

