### 1.2 Associations between Triple Negative Breast Cancer, BRCA Mutation Status, and DNA damaging chemotherapy

Recent studies illustrate the aggressive nature of triple negative breast cancer (TNBC), a subtype of breast cancer that is clinically negative for the expression of the estrogen and progesterone receptors (ER and PR) and the Her2 protein. The associations between basal-like breast cancer (BBC), TNBC and BRCA pathway dysfunction have apparent therapeutic implications. Although important to clarify that the terms “triple negative (TN)” and “basal-like” are not entirely synonymous, the clinico-pathologic TN (ER/PR/Her2 negative) phenotype is classified as basal-like via cDNA microarray 80-90% of the time. In addition, TNBC expresses a high proportion of “basal-like” cytokeratins (CK) 1, 10, 13, as well as p-cadherin and Her1/epithelial growth factor receptor (EGFR). As a clinically-applicable test for the basal molecular classification has yet to be developed, the triple negative phenotype is a reasonable surrogate for the basal-like subtype -- a subtype of breast cancer commonly seen among *BRCA1* mutation carriers. Moreover, a recent study of over 400 women reports TNBC among two-thirds of patients who carried a *BRCA1* mutation. The tight association between *BRCA1* mutations, BBC and TNBC has raised the question as to whether *BRCA1* loss of function through other mechanisms participates in the pathogenesis of sporadic basal-like and TNBC – an association which could be exploited therapeutically. Pre-clinically tumors that harbor BRCA mutations are more sensitive to DNA damaging chemotherapy agents such as cisplatin. Two recent clinical trials reported high pCR rates with cisplatin monotherapy regimens in patients with known BRCA mutations (72% in Gronwald et al, ASCO 2009, #502) or cisplatin in combination with bevacizumab in those with TNBC regardless of mutation status (36% in Ryan et al, ASCO 2009 #551). This pre-clinical and emerging clinical data supports the use of cisplatin in patients with TNBC who harbor substantial residual disease after standard neoadjuvant therapy.

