**Randomized Phase II – Arm A**

	Screening		Cycles 1-4	Post-treatment	Follow-up
	-30 days	-14 days	D1  (+/-3 days)	30-60 days from last treatment	+/-1 month
REQUIRED ASSESSMENTS					
Medical history	X				
Height	X				
Physical examination	X		X	X	X 
BP, weight	X		X	X	X 
ECOG performance status	X		X	X	X 
Blood Chemistries 		X	X	X	
Calculated creatinine clearance		X	X	X	
Platelets, ANC & Hgb		X	X	X	
Breast imaging					yearly
Electrocardiogram 	X		X		
MUGA or Echocardiogram	X				
Urine pregnancy or serum HCG 		X			
Adverse event and concomitant medication assessment	X		X	X	
TREATMENT					
Cisplatin			X		
CORRELATIVE STUDIES					
Tumor from diagnosis -Optional	X				
Tumor from definitive surgery -Mandatory	X				
Genomic DNA - Optional			X 		

1. Screening values obtained within 7 days of Day 1 do not need to be repeated prior to cycle 1 day 1.

2. Serum chemistries (creatinine, glucose, total protein, blood urea nitrogen [BUN], total carbon dioxide [CO2], albumin, total bilirubin, alkaline phosphatase, and aspartate transaminase [AST] and alanine transaminase [ALT]) and electrolytes (total calcium, chloride, potassium, sodium).

3. ECG will be done at baseline and prior to cycle 3. Additional ECG monitoring should be considered in patients who develop clinical significant electrolyte abnormalities during cisplatin therapy at the discretion of the treating physician.

4. Only in women of child bearing potential

5. If the genomic sample collection is missed at cycle 1 day 1, it can be collected at any time point during the study.

6. Every 4 months throughout years 1-2, then every 6 months for years 3-5.

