## 9.0 BIOLOGICAL CORRELATIVES

### 9.1 Central Pathology Reassessment

Analysis by an American Society of Clinical Oncology (ASCO) and College of American Pathology (CAP) expert panel suggests that approximately 20% of ER, PR, and HER2 tests performed in community laboratories are inaccurate with a fairly equal distribution of false positive and false negative results. While the ASCO/CAP guidelines seek to improve test quality and reliability, the impact of these recently published guidelines is not yet fully known. As such, a retrospective central reassessment of histological subtype, tumor grade, ER, PR, and HER2 will be performed by [name] for quality assurance and to confirm tumor phenotype. Tissue Microarrays (TMA) will be constructed to facilitate potential future correlative studies including genetic assessment of DNA damage repair pathways and potential gene expression profiles that might predict sensitivity to PARP inhibition.

Formalin-fixed paraffin-embedded (FFPE) tissue from biopsy at the time of initial diagnosis (optional) and from the residual disease removed at the time of definitive surgery (mandatory) should be sent within 30 days of randomization (or registration for patients enrolled to the safety run-in).

**NOTE:** Patients will be asked to consent to allow banking of their tumor samples for future correlative studies. Only tumor samples from consenting patients will be included in the TMAs.

Detailed instructions on sample collection, processing and shipping are outlined in the Study Procedures Manual.

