## 12.5 Analysis of Secondary Objectives

As support for the primary objective, overall DFS and 2-year DFS will be compared using the same techniques above using only the subjects in the randomized part of the study. One-year DFS will be tested using the test described above for 2-year DFS. Safety and tolerability variables will be tabulated separately for the two groups. Incidences of selected adverse events from the two treatment arms may be compared using Fisher's Exact tests on an exploratory basis. OS will be compared between treatment groups using the same methodology as DFS. PK levels will be described using summary statistics. In addition, characteristics of tumor specimens, and genomic DNA will be correlated with PARP inhibition, recurrence and toxicity. Continuous measures will be correlated with binary variables (e.g. recurrence and toxicity) using maximal chi-

square tests and continuous variables (e.g. PARP inhibition) using Pearson or Spearman correlations. Binary variables such as tumor and genomic characteristics will be correlated recurrence and toxicity using chi-square or Fisher's Exact test. All of the analyses with the PK and correlative data are exploratory and are designed to complement efforts in other trials with this agent.

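### The exploratory marker tests contain no arm term, so they cannot separate a prognostic or cisplatin-sensitivity marker from a marker of rucaparib benefit, although the randomised control arm would allow it

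*Combined protocol and SAP*

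**What the plan says.** The synopsis (Analysis of Secondary Objectives) and Section 12.5 carry nearly the same paragraph. It announces that "characteristics of tumor specimens and genomic DNA will be correlated with PARP inhibition, recurrence and toxicity". The methods follow:

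- Continuous markers: "Continuous measures will be correlated with binary variables (e.g. recurrence and toxicity) using maximal chi-square tests", with Pearson or Spearman correlation where the other variable is also continuous.
- Binary markers: "Binary variables such as tumor and genomic characteristics will be correlated recurrence and toxicity using chi-square or Fisher's Exact test".

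Neither place names the patients to be used, an arm, a within-arm analysis or a marker-by-arm term. Elsewhere in the same paragraph arm is explicit: safety is tabulated separately by group, and OS is compared between groups. The only multivariable model in the plan is the optional Cox regression of Section 12.4, which is for prognostic factors and adjusted treatment effects and has no interaction. The paragraph closes: "All of the analyses with the PK and correlative data are exploratory and are designed to complement efforts in other trials with this agent".

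Three other places bear on the point.

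- Section 1.2 says that, pre-clinically, "tumors that harbor BRCA mutations are more sensitive to DNA damaging chemotherapy agents such as cisplatin".
- Section 9.1 lists, among possible future uses of the tissue microarrays, "potential gene expression profiles that might predict sensitivity to PARP inhibition".
- The Arm A schedule includes "Tumor from definitive surgery -Mandatory", and Section 7.2.1 provides for an optional genomic DNA sample from all patients. The control-arm material will therefore exist.

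**The concern.** Whether a marker identifies patients who benefit from rucaparib is a question about how the treatment effect changes with the marker. A two-way table of marker against recurrence does not address it. Both arms receive the same cisplatin schedule, and the plan's own rationale expects BRCA-mutated tumours to respond better to cisplatin. Markers of DNA-repair deficiency, which are of most interest for a PARP inhibitor, are therefore the ones most likely to be associated with recurrence in both arms without any contribution from rucaparib.

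A time-to-event test of the marker alone would have the same gap, so this is separate from how censored follow-up is handled. For toxicity, a marker that acts only through rucaparib is diluted by Arm A patients if the arms are combined.

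At stake is how the correlative results can be read. They are meant to feed into other trials of the same drug, and a cisplatin or prognostic marker taken for a PARP-inhibitor marker would misdirect that work.

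**Working it through.** **1. The plan's own figure.** The documents give no figure for the marker analyses. The design figure that limits them is 38 DFS events (Section 12.1). Check of the hazard ratio: ln(0.632)/ln(0.40) = 0.501. Schoenfeld events, one-sided 0.10, 80% power, equal allocation: (1.2816 + 0.8416)² / (0.25 × (ln 0.5)²) = 37.53, rounded up to 38. The figure is reproduced.

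**2. Can the pooled table separate the two kinds of marker?** Assumptions: 50% marker prevalence (the documents give none), equal arms, and the plan's 40% control 2-year DFS placed in marker-negative controls. The event rate at 2 years in a cell with hazard ratio h against that group is 1 − 0.40^h.

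- (a) Purely predictive: no marker effect in control; rucaparib HR 1.0 in marker-negative and 0.25 in marker-positive patients.
- (b) Purely prognostic: marker HR 0.52 in both arms; rucaparib HR 0.5 in everyone.

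| 2-year event rate | Neg, control | Neg, rucaparib | Pos, control | Pos, rucaparib | Neg, pooled | Pos, pooled | Pooled odds ratio |
|---|---|---|---|---|---|---|---|
| (a) | 60.0% | 60.0% | 60.0% | 20.5% | 60.0% | 40.2% | 2.23 |
| (b) | 60.0% | 36.8% | 38.0% | 21.2% | 48.4% | 29.6% | 2.23 |

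Odds ratios (negative over positive): (0.600/0.400)/(0.402/0.598) = 2.23 and (0.484/0.516)/(0.296/0.704) = 2.23. The pooled association is the same. The control arm separates the two: 60% vs 60% in (a), 60% vs 38% in (b). The ratio of treatment HRs is 0.25 in (a) and 1 in (b).

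**3. How often would a non-predictive marker be flagged?** Simulation: 102 patients 1:1, exponential DFS, 18-month uniform accrual, cut-off at 30 months, 50% prevalence, two-sided 5%, 1,500 trials per scenario. Marker HR 0.5 in both arms, rucaparib HR 0.5 in everyone, no interaction.

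- Control hazard scaled so that average control DFS is 40% (about 45 events): pooled chi-square significant in about 56-60% of trials.
- 40% DFS placed in marker-negative controls (about 35 events): about 44-50%.
- Wald test of arm × marker in a Cox model: about 5% in either case.

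The pooled test is correct that the marker is associated with recurrence. The association carries no information about rucaparib.

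**4. How precise would the interaction be?** SE of the log ratio of HRs = √(sum of 1/events over the four marker-by-arm cells), with events split equally between arms. At 38 events and 50% prevalence, each cell has 9.5 events and SE = √(4/9.5) = 0.649. Power at one-sided 0.10 for a ratio of 0.5 = Φ(0.693/0.649 − 1.282) = 42%.

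| Marker prevalence (assumed) | SE | Power, ratio 0.5 | Power, ratio 0.25 | Smallest ratio with 80% power | Events for 80% power, ratio 0.5 |
|---|---|---|---|---|---|
| 50% | 0.649 | 42% | 80% | 0.25 | 151 |
| 30% | 0.708 | 38% | 75% | 0.22 | 179 |
| 20% | 0.811 | 34% | 67% | 0.18 | 235 |

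Only a very large interaction could be detected. Excluding the six cohort 2 patients, who are not randomised, leaves about 102 − 6 = 96 and lowers these figures somewhat.

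**The case against.** The best case for the plan has four parts.

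- **The text is silent on arm; it does not order pooling.** A reader might infer that the plan has decided to pool. It names test families without saying which patients enter them, and a within-arm chi-square would fit the wording. This stands. Silence still leaves the choice open until the data are seen, and nothing in the text leads to a marker-by-arm comparison.
- **The predictive aim belongs to later work.** The stated objective is to explore correlates of PARP inhibition, recurrence and toxicity, and the phrase about predicting sensitivity in Section 9.1 is attached to possible future studies. A reader might infer that the trial will report prognostic markers as correlates of rucaparib benefit. No passage says so. What remains is that the analysis as written could not support such a statement if someone made it.
- **The analyses are labelled exploratory.** No decision, sample size or stopping rule depends on them. This stands and sets the weight of the point. The label lowers the standard of proof but does not make a two-way test informative about treatment.
- **The interaction test is weak.** This also stands, and it limits what the remedy can claim.

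It is also tempting to say that the pooled test has less power for markers that are truly predictive. That is not generally so. With rucaparib HR 0.25 vs 1.0, 50% prevalence and no marker effect in control, the interaction test does better (about 55% against 45%). If the marker also has HR 0.7 in both arms, which the cisplatin rationale makes plausible, the order reverses: about 80% pooled against 42% for the interaction. At 20% prevalence without that effect it is 31% against 20%. The case rests on what each test measures and not on power.

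**Conclusion.** The point holds as a minor one on an exploratory analysis. The tests named for recurrence and toxicity have no arm term, no other section supplies one, and the resulting association cannot distinguish a prognostic or cisplatin-sensitivity marker from a marker of rucaparib benefit. The randomised control arm and its mandatory tissue make the distinction estimable.

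The equal pooled odds ratios in step 2 and the 44-60% against about 5% in step 3 illustrate the size. They rest on an assumed 50% prevalence, chosen marker effects, exponential DFS and 1:1 allocation, which the plan implies but does not state; the width of the 44-60% range comes mainly from how the control hazard is set. The primary DFS comparison is not affected.

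**What to change.** In Section 12.5 and the matching synopsis paragraph, add that, in randomised patients only (run-in cohorts excluded):

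- each marker will be examined in a Cox model for DFS and a logistic model for toxicity, with arm, marker and marker-by-arm interaction;
- the marker effect within each arm and the interaction will be reported with confidence intervals;
- any statement about sensitivity to PARP inhibition will rest on the interaction estimate;
- the analysis remains exploratory.

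The cost is about one sentence and a little more analysis, on samples already being collected. The downside is imprecision: at about 38 events, power for a ratio of HRs of 0.5 is about 34-42% at one-sided 0.10, so modest interactions will be missed. The results should be presented as estimates, and a non-significant interaction should not be read as evidence that a marker is not predictive.

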**SCHEMA**

PARP Inhibition after Preoperative Chemotherapy in Patients with Triple Negative Breast Cancer (TNBC) or ER/PR+, HER2 negative with Known BRCA1/2 Mutations: Hoosier Oncology Group BRE09-146

APatients must have triple negative (ER-/PR-/HER2-) breast cancer or if ER/PR + must have a known mutation of BRCA1 or BRCA2. Patients with HER2+ disease are excluded regardless of BRCA mutation status.

B Safety Run-in will be for the first 12 patients on study only (6 in cohort 1 and 6 in cohort 2). Patients in the safety run will be included in the efficacy analysis on intent to treat basis

CIf cycle 1 is well tolerated; the dose of rucaparib will be escalated from 16 mg to 24 mg for subsequent cycles in the cohort 1, and 24 mg to 30 mg in the cohort 2

**Arm A**

Cisplatin 75 mg/m^2 IV D1 every 3 weeks x 4 cycles

**Safety Run-in and Arm B**

Cisplatin 75 mg/m^2 IV D1 every 3 weeks x 4 cycles rucaparib 16-30 mg IV D 1,2,3 every 3 weeks x 4 cycles

Rucaparib maintenance 30 mg IV weekly OR 100 mg orally once weekly x 24 week's total

D Rucaparib will be escalated from 24mg to 30mg during the treatment phase of the study.

## 1.0 BACKGROUND & RATIONALE

### 1.1 Primary (neoadjuvant) Chemotherapy for Breast Cancer

Neoadjuvant chemotherapy has a well-established role in the management of both early-stage and locally advanced breast cancer. Providing treatment prior to definitive surgery not only improves the ability to achieve breast conservation, but also allows determination of *in vivo* sensitivity to therapy and offers an ideal platform for clinical research. Although many will experience shrinkage in tumor volume with neoadjuvant therapy, at the time of surgery only about 15-25% of patients will experience a pathologic complete response (pCR) with complete lack of invasive tumor tissue in the surgical specimen. Long-term follow-up of neoadjuvant studies consistently demonstrates significantly improved survival in individuals with pCR, with comparatively inferior outcomes in those with residual disease at surgery. The impact of residual disease is more striking in patients with triple negative (ER-/PR-/HER2-) disease compared to patients with other molecular phenotypes.

Unfortunately, patients with triple negative disease who have *substantial* (Miller-Payne classification 1 or 2 or residual cancer burden classification II or III) residual disease at the time of surgery have a dismal prognosis with only 35-40% remaining free of recurrence at 2 years. In short, the presence of viable invasive tumor after appropriate neoadjuvant chemotherapy reflects inherent resistance and portends an exceedingly high risk of subsequent recurrence. No standard therapy exists in this clinical setting.

### 1.2 Associations between Triple Negative Breast Cancer, BRCA Mutation Status, and DNA damaging chemotherapy

Recent studies illustrate the aggressive nature of triple negative breast cancer (TNBC), a subtype of breast cancer that is clinically negative for the expression of the estrogen and progesterone receptors (ER and PR) and the Her2 protein. The associations between basal-like breast cancer (BBC), TNBC and BRCA pathway dysfunction have apparent therapeutic implications. Although important to clarify that the terms “triple negative (TN)” and “basal-like” are not entirely synonymous, the clinico-pathologic TN (ER/PR/Her2 negative) phenotype is classified as basal-like via cDNA microarray 80-90% of the time. In addition, TNBC expresses a high proportion of “basal-like” cytokeratins (CK) 1, 10, 13, as well as p-cadherin and Her1/epithelial growth factor receptor (EGFR). As a clinically-applicable test for the basal molecular classification has yet to be developed, the triple negative phenotype is a reasonable surrogate for the basal-like subtype -- a subtype of breast cancer commonly seen among *BRCA1* mutation carriers. Moreover, a recent study of over 400 women reports TNBC among two-thirds of patients who carried a *BRCA1* mutation. The tight association between *BRCA1* mutations, BBC and TNBC has raised the question as to whether *BRCA1* loss of function through other mechanisms participates in the pathogenesis of sporadic basal-like and TNBC – an association which could be exploited therapeutically. Pre-clinically tumors that harbor BRCA mutations are more sensitive to DNA damaging chemotherapy agents such as cisplatin. Two recent clinical trials reported high pCR rates with cisplatin monotherapy regimens in patients with known BRCA mutations (72% in Gronwald et al, ASCO 2009, #502) or cisplatin in combination with bevacizumab in those with TNBC regardless of mutation status (36% in Ryan et al, ASCO 2009 #551). This pre-clinical and emerging clinical data supports the use of cisplatin in patients with TNBC who harbor substantial residual disease after standard neoadjuvant therapy.

### 1.3 PARP Inhibition

PARP is an abundant, constitutively-expressed nuclear enzyme that catalyzes the transfer of ADP-ribose polymers from NAD+ to target proteins, through which it facilitates DNA repair, cellular proliferation, and signaling to other critical cell cycle proteins and oncogenes. At sites of DNA damage, PARP activates intracellular signaling pathways that modulate DNA repair and cell survival through poly (ADP-ribosylation) of a number of nuclear proteins involved in the chromatin architecture and DNA metabolism. Immediate catalytic activation of PARP in response to DNA single- and double-strand breaks has been reported at levels up to 500-fold.

*BRCA1* and *BRCA2* genes encode for proteins critical for DNA integrity and genomic stability. *BRCA1* and *BRCA2* are tumor-suppressor proteins essential for cell division, DNA error control, DNA repair and apoptosis. In 2005 Bryant and Farmer showed that *BRCA*-deficient cells were extremely sensitive to PARP inhibition. Single agent PARP inhibitors led to impaired SSB repair causing double strand breaks (DSBs) in replicative cells. In *BRCA* wild type cells DSBs are repaired via homologous recombination (HR), but in *BRCA* “altered” cells HR is impaired and alternative pathways lead to complex rearrangements, loss of repair mechanisms and cell death (“synthetic lethality”). Significant single agent activity was recently reported with the PARP inhibitor olaparib in patients with previously treated *BRCA*-deficient metastatic breast cancer. Overall responses ranged from 22% (100 mg bid) to 41% (400 mg bid) with minimal toxicity.

Importantly, due to molecular and pathologic similarities between TNBC and *BRCA*-associated breast cancers, whose homologous recombination-dependent DNA repair is impaired, pharmacological inhibition of PARP is predicted to specifically and irreversibly augment the existing instability of these tumors.

In summary, there are at least three roles of PARP inhibitors in cancer treatment: chemotherapy and radiotherapy sensitization, synthetic lethality in patients with hereditary mutations in *BRCA1/2* genes (inherited defect in homologous recombination), and finally leveraging of “*BRCA*-like” defects tumors with spontaneous defects in DNA repair such as triple negative breast cancer.

